pregnant women. Treatment is commonly associated with headaches. Meta-analysis has suggested that treatment of hypertension with nifedipine may increase the risk of preeclampsia (OR 1.4 [1.06, 1.86])¹⁵ Treatment may be associated with a widened pulse pressure suggesting, with the incidence of headaches, that it may not be neuro-protective.¹⁶

Study Purpose

This trial will compare the efficacy, safety and side effects of these three oral regimens for management of severe hypertension in pregnant women. We hypothesize that nifedipine treatment of severe hypertensive parturient women is more effective than treatment with labetalol or methyldopa in controlling high blood pressure within six hours.

OBJECTIVES

Primary aim: To compare the efficacy of oral labetalol, oral nifedipine, and oral methyldopa for management of severe hypertension in pregnant women.

Secondary aims:

- To assess adverse outcomes and necessity for additional hypertensive treatment among women in the three study arms.
- To assess maternal and fetal outcomes among women in the three study arms

STUDY METHODS

Design

This is a pragmatic, open-label, randomised control trial of three oral anti-hypertensive regimens for women with severe hypertension in pregnancy. Women presenting with severe hypertension in pregnancy in two hospitals in Nagpur, India

will be randomised to one of three oral regimens: nifedipine, labetalol or methyldopa.

Study population

Pregnant women ≥ 18 years old and ≥ 28 weeks' gestation who have been determined to require pharmacological blood pressure control for severe hypertension defined as blood pressure $\geq 160/110$ mm of Hg, measured twice, 15 minutes apart with the woman sitting quietly for several minutes, the arm cuff at heart level, and diastolic pressure designated at the 5th Korotkoff sound, will be eligible for the trial. The relatively high entry criteria are chosen to avoid enrolling patients who might sufficiently improve without pharmacological treatment.

Two public hospitals in Nagpur, India – Government Medical College, Nagpur and Daga Women's Hospital, Nagpur – will be involved in this study. Together both hospitals have approximately 2,000 deliveries per month. Both hospitals have experience in the conduct of clinical trials, especially among this patient population. They encounter all the difficulties associated with low resource settings, but are also the site of an efficient and well run university department.

Number of Participants

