Successful outcome will be considered blood pressure that reaches the target (defined as 120-150mmHg systolic and 70-100 mmHg mm Hg diastolic) within 6h without an adverse outcome. Adverse outcomes include hypotension (systolic blood pressure, <120 mm Hg and/or diastolic blood pressure <70 mm Hg and fetal compromise), caesarean section for fetal distress within or up to 2 hours after the end of the study period, severe headache and severe headache requiring discontinuation of drug, or eclampsia.

Additional maternal outcomes:

- the number of BP measures above target range
- the number of BP measures below target range
- placental abruption
- maternal side effects associated with deteriorating maternal preeclampsia or the need to change drug regimen,
 - chest pain
 - dyspnea
 - headache
 - visual symptoms (flashes, diplopia)
 - epigastric or right upper quadrant abdominal pain

- nausea or vomiting.
- maternal mortality
- maternal morbidity during or up to two hours after the study period
 - eclampsia or seizure,
 - adverse CNS outcome (stroke, cortical blindness)
 - HELLP syndrome
 - pulmonary edema (O₂ sat < 90%, abnormal chest x-ray)
 - oliguria (<25 cc/hr for 2 hours)
 - disseminated intravascular coagulation
- Caesarean delivery
- Enrollment to delivery interval

Perinatal outcomes:

- stillbirth
- neonatal death
- admission to neonatal special care unit
- neonatal morbidity
 - Apgar < 7 at 5 minutes
 - intubation at place of delivery
 - mechanical ventilation beyond resuscitation
 - respiratory distress syndrome (RDS) requiring O₂ supplementation
 - abnormal cerebral ultrasound
 - convulsions
 - bradycardia (sustained HR < 100) beyond resuscitation and requiring intervention

Measures of the use of maternal health-care resources:

- number of days in the hospital
- admission to an intensive care unit or a high dependency unit
- mechanical ventilation (any)
- dialysis

- blood transfusion

Measures of the use of neonatal health-service resources:

- days in special care baby unit
- days of oxygen use
- days of mechanical ventilation

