Form 2: Monitoring Form (0-6h): This form will record the actual (rather than protocol) time for the administration of each dose. Assessment of blood pressure and pulse will be recorded every 20 minutes. Oxygen saturation will be measured and recorded every 2h. Maternal side effects including headache pain, nausea and vomiting, visual disturbances, urine output, right upper quadrant and epigastric pain will be assessed and recorded at the start of antihypertensive treatment (0h), 2h, 4h, and 6h. The Glasgow Coma Scale will be administered at 0, 2, and 6h by the attending research clinician. Although not specifically designed for this use, it is the best tool for assessment in this clinical environment. The utility of this tool for this trial will be assessed during the pilot study.

Form 3: Laboratory Results: This form will record the results of all laboratory tests. Liver enzyme tests, creatinine and platelet counts will be performed at 0h and 6 hours.

Form 4: Maternal Outcomes: The clinician will also note the final outcome of the woman including any interventions undertaken during labor and delivery. This information may be abstracted from patient charts if available.

Form 5: Neonatal Outcomes: The clinician will also note the final outcome of the baby including any interventions undertaken during labor and delivery. This information may be abstracted from patient charts if available.

Form 6: Exit Interview: The interview with the woman will be conducted once she is stable and prior to her discharge from the study hospital. This form will record her attitudes and opinions regarding the mode of treatment including experience with pain and side effects.

Form 7: Case Summary. Clinicians will complete a case summary form for each woman after she is discharged from the study. The form will summarize data recorded on other forms and confirm the number of doses administered, adverse events, and treatment discontinuation.

STATISTICS AND DATA ANALYSIS

Sample Size Calculation

The primary outcome will be control of high blood pressure (defined as 120-150mmHg systolic and 70-100 mm Hg diastolic) within 6h.

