The study results will be published in an international medical journal at the end of the study, and presented at international professional and medical research meetings. The final publication will be open access. Study results will also be disseminated on the Gynuity websites and in in-house publications, including Gynuity's research briefs, both of which are designed to make scientific results accessible to a lay audience. In India, study findings will be presented at the annual meetings of the state and national conferences of the Federation of Obstetricians and Gynaecologists of India (FOGSI).

Intellectual Property/Commercial Exploitation

This research does not use any technology or other invention that is participant to patents or other forms of intellectual property protection. The proposed research will be conducted by a collaboration of three organizations and contracts will be drawn up between all relevant parties. The data could be used to register a new indication for the drugs involved in the trial, but the study team deems this unlikely given that all three drugs are already widely currently used. The study does not require the collection of any tissues or samples from human participants.

PHARMACOVIGILANCE

Risks to the Participants

Treatment with any antihypertensive medication is associated with the risk of hypotension or low blood pressure. These risks are extensions of the beneficial effects of the medications – treatment of hypertension, high blood pressure. Symptoms associated with low blood pressure may include dizziness, light headedness and fatigue. Low blood pressure can potentially adversely affect the fetus due to poor utero-placental perfusion associated with hypotension. These are, in general, dose dependent complications. Patient will be treated in a hospital

environment with close monitoring of blood pressure. To address the possibility of excessive under-treatment, aggressive oral regimens have been designed. The clinical team will remain "in charge" and have the autonomy to address issues of clinical under-treatment or concerns regarding impending over treatment.

The drug of choice for management of severe hypertension in pregnancy at the study sites is oral nifedipine 10mg-20mg. Headache is a common complication of treatment of blood pressure with medications that are pure vasodilators. Treatment with nifedipine is associated with the development of headaches (12-16%).^{18,19}

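### The scheduled 0–6h symptom list (Form 2) does not name chest pain or dyspnea, both listed outcomes, or the low-blood-pressure symptoms the protocol links to any antihypertensive

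*Protocol*

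**What the plan says.** Study Purpose in the protocol states: "This trial will compare the efficacy, safety and side effects of these three oral regimens".

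Study Outcomes, under the additional maternal outcomes, has an item for "maternal side effects associated with deteriorating maternal preeclampsia or the need to change drug regimen". Six symptoms stand beneath it: chest pain, dyspnea, headache, visual symptoms, epigastric or right upper quadrant pain, and nausea or vomiting.

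The description of Form 2 (0–6h) in Study Assessment and Data Collection Forms says: "Maternal side effects including headache pain, nausea and vomiting, visual disturbances, urine output, right upper quadrant and epigastric pain will be assessed". It sets these assessments at 0, 2, 4 and 6 hours. Study Interventions describes the same side-effect assessment without naming symptoms and sets it at 0, 2 and 6 hours.

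Risks to the Participants opens with "Treatment with any antihypertensive medication is associated with the risk of hypotension or low blood pressure" and continues: "Symptoms associated with low blood pressure may include dizziness, light headedness and fatigue". The same section attributes headache to nifedipine, at 12–16%.

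**The concern.** A comparison of side effects between arms depends on every woman being asked the same questions at the same times. The protocol names two symptoms as outcomes and three more as expected effects of over-treatment, yet none of the five appears in the description of the one timed symptom assessment. If the form follows that description, these symptoms will reach the data only when a woman volunteers them, a clinician notes them, or they are recalled at the exit interview.

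The trial is open-label, so what gets volunteered or noted may depend on knowing the drug. No analysis plan can repair this afterwards: a symptom not asked about between 0 and 6 hours cannot be recovered, and its absence from the record cannot be told apart from its not having occurred. A symptom not asked about at 0h also has no baseline. That matters here because women enter with severe hypertension and may already have symptoms of their disease.

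**Working it through.** No sample-size or power figure is involved. The check sets the lists side by side.

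| Symptom | Outcome (Study Outcomes) | Low-blood-pressure symptom (Risks to the Participants) | Named for Form 2 |
|---|---|---|---|
| Headache | yes | no | yes |
| Visual symptoms | yes | no | yes |
| Epigastric / right upper quadrant pain | yes | no | yes |
| Nausea or vomiting | yes | no | yes |
| Chest pain | yes | no | **no** |
| Dyspnea | yes | no | **no** |
| Dizziness | no | yes | **no** |
| Light headedness | no | yes | **no** |
| Fatigue | no | yes | **no** |

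Form 2 also names urine output, which is a measurement and matches the separate oliguria outcome.

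Counts: symptom outcomes not named for Form 2, 6 − 4 = 2 of 6. Hypotensive symptoms not named, 3 − 0 = 3 of 3. None of those three is an outcome either.

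Next, whether another route collects the missing items:

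- **Form 2, signs.** Blood pressure and pulse are recorded every 20 minutes and oxygen saturation every 2 hours. These capture hypotension and desaturation as signs. They do not record whether the woman was dizzy or breathless, and dyspnea is an outcome in its own right.
- **Form 3.** Liver enzymes, creatinine and platelets at 0 and 6 hours; no symptoms.
- **Form 4.** Final maternal outcome and interventions, possibly abstracted from charts; no named symptoms.
- **Form 6.** An interview before discharge covering side effects in general. It relies on recall. Under Study Interventions, methyldopa women not at goal at 6 hours go on to nifedipine or labetalol, so a recalled symptom may belong to the second drug.
- **Form 7.** Completed after the woman leaves the study. It summarises the other forms and confirms doses, adverse events and discontinuation.
- **Stopping reasons.** Recorded when treatment is discontinued, so they cover only side effects severe enough to stop it.
- **Adverse-outcome composite.** It contains "Adverse outcomes include hypotension (systolic blood pressure, <120 mm Hg and/or diastolic blood pressure <70 mm Hg and fetal compromise". If fetal compromise is read as qualifying the pressure limits, low maternal pressure with symptoms but without fetal compromise does not count.

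None of these asks every woman about the five symptoms at set times.

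The two schedules for the side-effect assessment also disagree: three time points in Study Interventions (0, 2, 6h) and four in the Form 2 description (0, 2, 4, 6h).

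**The case against.** The strongest reply is that the quoted sentence is a one-line summary introduced by a word that leaves the list open, and that the form itself is not shown. Trial Management has study materials prepared to match the protocol, and the protocol does name chest pain and dyspnea. This stands to a degree: absence from the description does not prove absence from the form. It does not dispose of the point. The person building the form works from this list, and a named outcome should not depend on its unstated remainder. For the hypotensive symptoms there is not even an outcome entry to prompt inclusion.

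It can also be said that a risk paragraph does not commit the trial to measuring every symptom it mentions. That is fair. Making the hypotensive symptoms outcomes is an improvement in line with the stated purpose, not the repair of a broken promise. Chest pain and dyspnea are different, since they are already outcomes.

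Two stronger readings are tempting, and the protocol supports neither.

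- A reader might infer that headache is the only drug effect collected. It is not. Hypotension is measured, counted through readings below target and included in the composite. Oxygen saturation and liver tests are the protocol's stated monitoring for the labetalol and methyldopa risks. Headache is only the one *symptom* named for Form 2 that the protocol attributes to a study drug.
- A reader might infer that the side-effect comparison is tilted against nifedipine, because its headache is asked about and also enters the composite ("severe headache and severe headache requiring discontinuation of drug, or eclampsia"). But the omitted hypotensive symptoms are attributed to all antihypertensives, so leaving them out could hide nifedipine effects as well. Chest pain and dyspnea are not attributed to labetalol or methyldopa. Headache is assessed at 0h in every arm. The quoted rate implies 298 × 0.12 = 35.8 to 298 × 0.16 = 47.7, or about 36 to 48 nifedipine women with headache. That is an expected count of headaches, not a count of missed or misattributed events.

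**Conclusion.** The point holds as a gap in systematic symptom collection: 2 of 6 listed symptom outcomes and 3 of 3 hypotensive symptoms have no named place in the only timed symptom assessment, although comparing side effects is a stated purpose. It is not a demonstrated bias for or against any arm, and neither the direction nor the size of one can be derived from the protocol. The primary blood pressure target and the sample size are unaffected.

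The conclusion assumes that Form 2 follows its description. If the form already carries these items, what remains is a correction to the text together with the conflict between the two assessment schedules. The change is worth making before enrolment because it is cheap and the data cannot be obtained later.

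**What to change.** 1. In the Form 2 description, and on the form, name chest pain, dyspnea, dizziness/light headedness and fatigue as yes/no items asked of every woman at each scheduled side-effect assessment, including 0h.
2. In Study Outcomes, add dizziness/light headedness and fatigue to the maternal side-effect outcomes, reported as new or worse than at 0h, so that symptoms arising on treatment are separated from those present at entry.
3. Reconcile the assessment times in Study Interventions (0, 2, 6h) with those in the Form 2 description (0, 2, 4, 6h), so that all arms and both hospitals follow one schedule.

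The cost is four tick boxes at assessments already planned. The downside is a slightly longer checklist.

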We hypothesize that nifedipine treatment of hypertensive parturient women will be more effective than labetalol or methyldopa in controlling high blood pressure (defined as 120-150mmHg systolic and 70-100 mm Hg diastolic) within 6h. Brown et al found that 83% of pregnant women with severe hypertension treated with nifedipine had successful lowering of blood pressure 110 to 169/80 to 109 mm Hg by 90 minutes without an adverse outcome.¹⁷ Our trial will enroll sicker patients and our goal is lower and lasting control. Based on the (scant) available literature, we hypothesize that nifedipine will control 75% of high blood

pressure within 6 hours and labetalol and methyldopa will be able to control 62.5% and 62.5%, respectively. As the subjects in the nifedipine study group will serve as a comparison group for both the labetalol and methyldopa regimens, the comparison of labetalol and nifedipine requires a sample size of 261 in each study group given a two tailed test, $\alpha=0.05$ and $1-\beta=80\%$, and a simple Bonferroni correction. Using the same statistical assumptions, with a nifedipine sample size of 261, the methyldopa study group requires 261 subjects. In order to account for loss to follow-up, we will enroll 894 women total (nifedipine: 298 women; labetalol: 298 women; methyldopa: 298 women).

Proposed Analyses

After the data are entered, they will be converted into an SPSS for Windows data file, reviewed for logical inconsistencies, cleaned, and analyzed.

For each of the regimens, we will calculate the following statistics:

- % of women who reach the target (defined as 120-150mmHg systolic and 70-100 mmHg mm Hg diastolic) within 6h without any specified adverse outcome (see above)
- % of women who reach the target (defined as 120-150mmHg systolic and 70-100 mmHg mm Hg diastolic) within 3h without any specified adverse outcome (see above)
- % of women who experience an adverse outcome. Adverse outcomes include hypotension (systolic blood pressure, <120 mm Hg and/or diastolic blood pressure <70 mm Hg and fetal compromise), caesarean section for fetal distress, severe headache or eclampsia.

- % of women who reach an intermediate target (defined as 120-159 mmHg systolic and 70-104 mmHg diastolic) within 6 hours without an adverse outcome.
- % of time systolic and diastolic blood pressure in target range

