At each hospital, patient files will be kept in locked cabinets with all identifying information removed. Signed informed consent forms will also be kept in locked cabinets, separate from the patient files. Only authorized study personnel will have access to these files. The original copy of all study forms will be sent to Gynuity Health Projects on a monthly basis and photocopies of each form will be maintained at each study hospital for five years.

Confidentiality

All evaluation forms and records will be identified using a coded number to maintain participant confidentiality. All records will be kept in a locked filing cabinet at the study hospital. Clinical information will not be released without the permission of the participant, except as required for monitoring by Gynuity Health Projects.

Data Monitoring Committee

An independent Data Safety Monitoring Board (DSMB) will be established to oversee the safety of participants in the trial. The terms of reference of the DSMB will be developed separately, based on the principles developed by the DAMOCLES group.

For safety purposes, interim analyses will be conducted when approximately half of the study sample have been enrolled (n=447). Recommendations will be made based on any findings of differences in primary outcomes or adverse events between the three study groups. The Haybittle–Peto boundary will guide the interim analysis and statistical stopping approach: If the interim analysis shows a probability of less than 0.001 that the primary outcome of the three treatments are different, then the trial will be stopped early. It is possible that only one arm might be discontinued without the need to discontinue the entire trial in the event of a safety issue in that arm.

As indicated above, the primary outcome is defined as the % of women who reach the target (defined as 120-150mmHg systolic and 70-100 mmHg mm Hg diastolic) at 6h without any specified adverse outcome.

REPORTING, PUBLICATIONS AND NOTIFICATION OF RESULTS

Data Policy

The data from this study will be confidential until the database is closed at the end of the study. Following this the study investigators will have exclusive access to the data until the publication of the results in a journal. The consent form will include a clause for the woman to give permission for her anonymous data to be used for future research studies.

Publication

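### The sample-size section and the Data Monitoring Committee section define the primary outcome differently, so the 80% power is not shown to apply to the composite endpoint

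*Protocol*

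**What the plan says.** The protocol describes success in four places, and they do not agree.

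- **Sample Size Calculation:** "The primary outcome will be control of high blood pressure (defined as 120-150mmHg systolic and 70-100 mm Hg diastolic) within 6h". There is no adverse-outcome condition. The planning rates follow in the same language: "Based on the (scant) available literature, we hypothesize that nifedipine will control 75% of high blood" pressure within 6 hours, and 62.5% for each of labetalol and methyldopa.
- **Data Monitoring Committee:** "As indicated above, the primary outcome is defined as the % of women who reach the target", with the qualifier "at 6h without any specified adverse outcome". The section presents this as already indicated earlier in the document.
- **Study Outcomes:** a successful outcome is reaching the target "within 6h without an adverse outcome. Adverse outcomes include hypotension" and other events, among them "severe headache and severe headache requiring discontinuation of drug, or eclampsia".
- **Proposed Analyses:** the first listed statistic is the percentage reaching target within 6h free of any specified adverse outcome.

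Only the first two use the term primary outcome. The first omits the adverse-outcome clause and the second includes it. The time wording also differs: within 6h everywhere except the Data Monitoring Committee section, which says at 6h.

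The only literature rate given for nifedipine is 83%. It is described as lowering of blood pressure by 90 minutes without an adverse outcome. The protocol expects less than this because its patients are sicker and its goal is lower and lasting.

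**The concern.** A woman whose pressure reaches target but who has a severe headache, or a caesarean for fetal distress, is a success under the sample-size wording and a failure under the Data Monitoring Committee wording. Following the plan could therefore give two different primary results. The interim stopping rule is attached to the composite, while the sample size is argued from control.

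The power statement has the same weakness. If 75% and 62.5% are rates of control alone, the composite success rates are lower in every arm where adverse outcomes occur, and the 12.5-point difference need not carry over. A null result on the composite could then be reported against an 80% power worked out for a differently defined outcome.

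**Working it through.** **Inputs from the protocol (Sample Size Calculation).** p1 = 0.75 (nifedipine); p2 = 0.625 (each comparator); two-sided α = 0.05 with a simple Bonferroni correction, taken as two comparisons with nifedipine, so 0.025 each; power 80%; 261 per arm, 298 enrolled per arm, 894 in total.

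**Step 1: reproduce the stated figure.** Pooled-variance formula without continuity correction, where p̄ = (p1 + p2)/2:

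n = [z(α/2)·√(2p̄(1−p̄)) + z(β)·√(p1(1−p1) + p2(1−p2))]² / (p1−p2)²

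With z(α/2) = 2.241, z(β) = 0.842 and p̄ = 0.6875:

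n = [2.241 × 0.6555 + 0.842 × 0.6495]² / 0.125² = [1.469 + 0.547]² / 0.015625 ≈ 260.1, rounded up to **261**.

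This matches the protocol. The power at 261 per arm is

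Φ{ [|p1−p2|·√n − z(α/2)·√(2p̄(1−p̄))] / √(p1(1−p1) + p2(1−p2)) } = Φ(0.847) = **80.2%**.

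**Step 2: if 75% and 62.5% are already composite rates.** Nothing changes: 261 per arm and 80.2%.

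**Step 3: if they are control-only rates.** Composite success in an arm is the control rate × (1 − adverse-outcome rate among controlled women). The protocol gives no such rates, so those below are assumptions chosen to show the range. The same power formula is used, with n = 261 and α = 0.025.

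| Assumed adverse rate, nifedipine / comparator | Composite success | Difference | Power |
|---|---|---|---|
| 0% / 0% | 75.0% v 62.5% | 12.5 points | 80% |
| 2% / 2% | 73.5% v 61.25% | 12.25 | 77% |
| 5% / 5% | 71.25% v 59.4% | 11.9 | 73% |
| 10% / 10% | 67.5% v 56.25% | 11.25 | 66% |
| 5% / 2% | 71.25% v 61.25% | 10.0 | 57% |
| 5% / 0% | 71.25% v 62.5% | 8.75 | 45% |
| 2% / 5% | 73.5% v 59.4% | 14.1 | 88% |

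Example for 5% / 2%: 0.75 × 0.95 = 0.7125 and 0.625 × 0.98 = 0.6125. Then p̄ = 0.6625, and the argument of Φ is (0.10 × 16.155 − 2.241 × 0.6687)/0.6650 = 0.175, which gives 57%.

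**What the table shows.** Equal adverse rates cost some power, because the difference shrinks in proportion. A nifedipine excess costs much more, and a comparator excess can raise power above 80%. The net difference alone does not fix the answer: 0%/0% and 5%/5% have the same net difference and give 80% and 73%.

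If all 298 per arm were analysed, power would be 79% for 5%/5%, 63% for 5%/2%, 51% for 5%/0% and 92% for 2%/5%.

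**The case against.** The strongest reply is that the short wording is shorthand and the rates are composite rates throughout. The 83% behind the nifedipine assumption already excludes women with an adverse outcome. The reasons given for lowering it are sicker patients and a stricter goal; nothing says that adverse outcomes were put back in. The Data Monitoring Committee section presents its definition as a restatement of what came before. On that reading the power is 80.2% and only the wording is loose. This reading is possible and cannot be ruled out. It is not stated, however, and the 62.5% for the comparators has no cited rate behind it of either kind.

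In the other direction, a reader might infer that the stated power is simply wrong for the primary endpoint, and that the loss falls on nifedipine because Risks to the Participants gives a 12-16% headache rate for it. The documents do not support that:

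- The 12-16% is any headache; the composite counts severe headache. The protocol gives no severe fraction.
- Labetalol is said to have few side effects, but no rate of the composite's adverse outcomes is given for labetalol or methyldopa.
- Study Outcomes also lists headache among effects of deteriorating preeclampsia, so poorer control could produce more of it in the comparator arms. Eclampsia and caesarean for fetal distress are not specific to nifedipine.
- A calculation that lets only nifedipine lose successes assumes zero adverse outcomes in the comparators.

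Neither the size nor the direction of any change in power can therefore be read from the protocol.

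**Conclusion.** The contradiction in the primary outcome stands, both on the adverse-outcome clause and on within 6h against at 6h. As a consequence, 80% power at 261 per arm is not shown to apply to the composite. This is a fault of definition, not of arithmetic: the 261 is correct for the rates entered.

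The size is conditional. There is no loss if 75% and 62.5% are net of adverse outcomes. If they are not, power runs from 45% (5%/0%) to 88% (2%/5%) across the unequal assumed rates shown, with 73% for 5% in both arms. These figures rest on assumed adverse-outcome rates, on the proportional-loss model, and on a Bonferroni correction for two comparisons. They illustrate sensitivity and do not estimate this trial's power.

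**What to change.** 1. Use one composite definition of the primary outcome in Sample Size Calculation, Proposed Analyses and the Data Monitoring Committee section, consistent with Study Outcomes.
2. Reconcile within 6h with at 6h, so that the final and interim analyses use the same endpoint.
3. State whether 75% and 62.5% are net of adverse outcomes. If they are, one sentence settles the matter and the 80% stands.
4. If they are not, state an assumed adverse-outcome rate for each arm and restate the power at 261 per arm over a grid of both arms' rates, including cases where the comparators do worse. A table of net differences alone would not be enough, because the power depends on both rates.

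The 894 need not change. The cost is wording and possibly a less favourable stated power.

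### Optional efficiency gain, not an error: if the sizing Bonferroni correction is carried into the final analysis, Holm's step-down test would recover power within the same 5% familywise limit

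*Protocol*

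**What the plan says.** The Sample Size Calculation states that "the nifedipine study group will serve as a comparison group for both the labetalol and methyldopa regimens", so there are two primary comparisons with a common arm. Nifedipine is assumed to succeed in 75% of women, while "labetalol and methyldopa will be able to control 62.5% and 62.5%, respectively". The stated conditions are "given a two tailed test, $\alpha=0.05$ and $1-\beta=80\%$, and a simple Bonferroni correction". On that basis "the comparison of labetalol and nifedipine requires a sample size of 261 in each study group", and "with a nifedipine sample size of 261, the methyldopa study group requires 261 subjects". Enrolment is then raised to 298 per arm (894 in all) for loss to follow-up.

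The Bonferroni phrase, "and a simple Bonferroni correction", occurs only there, as an input to the sizing. Proposed Analyses describes regression models with 95% confidence intervals and an intention-to-treat primary analysis. It does not say how the two nifedipine comparisons will be adjusted for multiplicity. The Data Monitoring Committee section plans an interim analysis of the primary outcome at 447 women.

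**The concern.** Under simple Bonferroni each comparison is tested at 0.025 whatever the other shows. Holm's procedure tests the smaller p-value at 0.025 and, if that is significant, tests the other at 0.05. It rejects whenever Bonferroni does, sometimes rejects the second hypothesis as well, and holds the familywise error at or below 5% under any dependence, so the shared arm is no obstacle. It needs only the two p-values and therefore works with whichever regression model is chosen.

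Study Purpose and the Sample Size Calculation both hypothesise that nifedipine does better than the other two drugs. Readers will care about both contrasts, and the second is where a single-step rule loses power. What is at stake is the chance of missing one of two real 12.5-point differences in a trial whose size is already fixed.

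**Working it through.** **Inputs (Sample Size Calculation).** p0 = 0.75 (nifedipine); p1 = p2 = 0.625 (labetalol, methyldopa); difference d = 0.125; two-sided alpha 0.05; power 0.80; 261 evaluable and 298 enrolled per arm.

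**1. Reproduce 261.** Pooled variance, no continuity correction:

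n = [z(1−α/2)·√(2·p̄·q̄) + z(0.80)·√(p0·q0 + p1·q1)]² / d²

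- p̄ = 0.6875, so √(2 × 0.6875 × 0.3125) = 0.6555.
- √(0.1875 + 0.2344) = 0.6495.
- At α = 0.05/2 = 0.025: (2.2414 × 0.6555 + 0.8416 × 0.6495)² / 0.015625 = 260.1, which rounds up to **261**, an exact match.
- At α = 0.05 the same formula gives 215, and at 0.05/3 it gives 287.

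The correction is therefore a division by two, for these two comparisons.

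**2. Power under each rule, normal approximation, 261 per arm.**

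- The shared arm gives a correlation of 0.1875 / 0.421875 = 0.444 between the two estimated differences.
- Power at 0.025 is 80.2%, and both comparisons are significant at 0.025 with probability 68.3%.
- The probability that one named comparison passes 0.025 and the other passes 0.05 is 73.0%.
- Holm, per comparison: 80.2 + 73.0 − 68.3 = 84.9%.
- Holm, both: 2 × 73.0 − 68.3 = 77.7%.

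**3. Simulation.** Binomial three-arm trials, pooled z-tests, critical values 2.241 and 1.960:

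| Protocol rates | Bonferroni | Holm |
|---|---|---|
| 261 per arm, each comparison | 80.4% | 84.9% |
| 261 per arm, both | 69.2% | 78.3% |
| 261 per arm, at least one | 91.6% | 91.6% |
| 298 per arm, each comparison | 85.6% | 89.5% |
| 298 per arm, both | 76.6% | 84.4% |

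Holm reaches 80% per comparison with about 232 per arm, so the gain is worth about 261 − 232 = 29 women per arm.

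**4. When the gain disappears or grows (261 per arm).**

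- If only one effect is real (75% v 62.5%, third arm at 75%), its power moves from about 80.4% to 80.5%.
- If methyldopa succeeds in only 50% (an assumption; the Pilot Study section voices doubt about its potency, but the sizing uses 62.5%), nifedipine v labetalol goes from 80.4% to 87.2%.

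**5. Familywise error.**

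- Both nulls true: 4.6% to 4.7% under either rule.
- One null true: 2.5% for Bonferroni; for Holm, 4.2% at 261 per arm and 4.4% at 298.
- One null true and the other comparison nearly certain: Holm uses almost the whole 5%.

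**6. What the extra wins look like.** Holm's additional rejections have p between 0.025 and 0.05. They occur in 78.3 − 69.2 = about 9% of trials at 261 per arm and 84.4 − 76.6 = about 8% at 298. In nearly all of them the 97.5% interval for that difference includes zero.

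The calculations ignore covariate adjustment and the interim look.

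**The case against.** The strongest reply is that nothing here is wrong. Bonferroni is valid, the sample size reproduces exactly and the promised 80% per comparison is met. Choosing between two valid procedures is a matter of preference. The phrase is a sizing input and not a final-analysis rule, and an analysis plan that is not shown could already specify Holm. All of this stands, and it is why the point is optional.

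A reader might go further and infer that the trial is underpowered because showing both differences has only a 69% chance. The protocol does not support that. It powers each comparison separately and sets neither a joint-power target nor a requirement to win both. If success did require both, each could be tested at 0.05 with no correction, giving 79.0% for both at 261 per arm, slightly above Holm. If either result counts on its own, Holm leaves the chance of at least one success unchanged.

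A reader might also take Holm's error rate to be identical to Bonferroni's. It shares the 5% ceiling, but with one null true it uses more of it. Finally, 261 assumes the whole loss allowance is used up. With a six-hour in-hospital endpoint the evaluable number may be nearer 298, where the absolute gains are a little smaller. No loss rate is given, so both are shown.

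None of this removes Holm's dominance as a test: it never rejects less, stays within the limit and needs no extra women.

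**Conclusion.** The point holds as an inexpensive improvement. The stated method and sample size are sound, so it is not a defect in the plan. The loss occurs only if the sizing correction becomes the rule for the final tests, which the protocol neither states nor excludes. In that case, under the protocol's own success rates, Holm adds about 4.5 points per comparison and 9 points for both at 261 per arm, and about 4 and 8 points at 298. These gains rest on both 12.5-point effects being real and on the family being the two nifedipine comparisons. Adding labetalol v methyldopa would change the figures.

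**What to change.** Keep the Bonferroni-based sample size. Add one sentence to Proposed Analyses saying that the two primary comparisons, nifedipine v labetalol and nifedipine v methyldopa, will be tested by the Holm step-down procedure at a two-sided familywise level of 5%. Settle this before any comparative data are seen, including the interim analysis at 447 women.

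Report 97.5% confidence intervals for these two differences, because intervals matched to Holm are awkward to construct. State the downside openly: a comparison won only at the second step (p between 0.025 and 0.05) will ordinarily have a 97.5% interval that includes no difference, and the report should say so. This matters because Proposed Analyses is built around estimates with intervals. The cost is the added text and that presentational mismatch; no extra women or data are needed.
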